**Proprietary confidential information.**

© 2015 Boehringer Ingelheim International GmbH or one or more of its affiliated companies. All rights reserved.

This document may not - in full or in part - be passed on, reproduced, published or otherwise used without prior written permission.

as well as the logarithm of the treatment exposure as an offset. In all analyses of annualised rate of event, the length of the event will be subtracted from the extent of exposure or the length of the observation period because one cannot expect to have another event during an event. Moderate to severe COPD exacerbations occurring within 1 day (i.e.: 24 hours) after the last drug administration date are included in the primary analysis.

### 7.3.2 Secondary analyses

For the key secondary endpoint, i.e., time to the onset of the first moderate to severe COPD exacerbation, as well as other time to event endpoints (see [Section 5.1.1](#)), a Cox's proportional hazard model will be used to estimate the hazard ratio and the corresponding 99% confidence intervals, while log-rank test will be used to obtain the p-value for testing the survival curves. For other annualised rate of event endpoints (see Section 5.1.1), the same negative binomial model as specified for the primary endpoint will be used.

For all efficacy analyses including time to all-cause mortality the treated set (on-treatment + 1 day) will be used.

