### 5.1.2.3 Assessment all-cause mortality

Death from any cause includes cardiovascular death, non-cardiovascular-death and undetermined cause of death, as classified by adjudication. For all patients (completed/discontinued) vital status collection time of interest will be the planned 52-week + 21 days starting from visit 2.

Further details on death classification will be specified in the mortality adjudication charter.

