#### **5.2.2 Secondary endpoints**

Secondary endpoints are defined in the revised CTP, Section 5.1. They are:

- Annualized rate of exacerbation leading to hospitalization during the actual treatment period.
- Time to first COPD exacerbation leading to hospitalization during the actual treatment period.
- Time to all-cause mortality occurring during the actual treatment period.

All deaths are adjudicated by a blinded and independent adjudication panel to determine the primary cause of death.

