## 6. GENERAL ANALYSIS DEFINITIONS

### 6.1 TREATMENTS

As described in Section 4 of the revised CTP, patients will be randomized in equal allocation to one of two treatment groups delivered by the Respimat® inhaler:

- Tiotropium + olodaterol fixed dose combination (FDC) (5µg / 5µg) inhalation solution once daily
- Tiotropium (5 µg) inhalation solution once daily.

Table 6.1: 1 Treatments and their labels

Treatment	Short label
Tiotropium + olodaterol FDC (5 µg / 5 µg) inhalation solution	T+O 5/5
Tiotropium (5 µg) inhalation solution	Tio 5

The trial consists of a 360 days of treatment followed by a 21 day residual effect period.

For analysis purposes the following periods are defined:

- Planned study period  
The planned study period is defined as 360 days of treatment + 21 days of follow up after the administration of the first dose of trial medication according to the CTP flow chart.
- Planned treatment period  
The planned treatment phase is defined as 360 days of treatment + 1 day for wash-out according to the CTP flow chart.
- Actual treatment period  
The actual treatment period is defined as the interval from first in-take of study medication until 1 day after last in-take of study medication.
- On-treatment period  
The on-treatment period is defined as the interval from first in-take of study medication until 21 days after last in-take of study medication.

Patients that discontinue early will be monitored for exacerbations and vital status until they have reached the end of their planned study period.

Table 6.1:2 Analyses performed within each period

Types of Analyses to be performed	Periods			
	Actual treatment period (Treatment +1 day wash-out)	Planned treatment period (includes 1 day wash-out)	Planned study period (includes residual effect period of 21 days)	On-treatment period (includes residual effect period of 21 days after last drug intake)
Primary Exacerbation analysis	✓			
Sensitivity primary exacerbation analysis		✓		
Key secondary exacerbation analysis	✓			
AE safety analysis				✓

Patients will be analyzed according to the treatment group of the first treatment received. Potential treatment switcher scenarios caused by treatment misallocation will be discussed at the Blinded Report Planning Meeting (BRPM). After database lock (DBL) patients who fall into these discussed scenarios will be analyzed according to meeting decisions.

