### Last known date alive

The date of last known day alive is determined as the latest date among: the final vital status date (defined as the assessment date if alive, or date last known alive if 'unknown'), the date of first dose of study medication, the date of last drug administration, all the visit dates (including phone contact dates in which the patient was reached and follow-up contact dates) and start or stop dates of events reported on the adverse event forms.

If a patient dies, the date of death is the last date known alive.

[figure not shown]

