**Survival time calculations:**

A. Actual treatment event analysis: Events (death or exacerbation) are counted in the actual treatment time to event analysis whenever they occur between the first dose of randomized treatment and one day after treatment discontinuation (i.e. during the actual treatment period) (see [section 6.1](#)).

Patients with no event observed during the actual treatment period will be censored at date of last dose of randomized study drug administration (i.e. treatment discontinuation) +1 day.

Time at risk:

- *Patients with event counted:* (<date of event> – <date of first drug administration> +1).
- *Patients without event counted:* (<date of last dose of study drug> – <date of first drug administration > +1) + 1 day wash-out

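### The visible mortality hazard ratio stops at last dose + 1 day although vital status is collected to the end of the planned study period; a full-period analysis should be named beside it

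*Protocol*

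**What the plan says.** On the analysis window the two documents agree.

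- Protocol 5.1.1 defines the mortality endpoint as death up to 1 day after the last drug administration. Protocol 7.3.2 repeats the window: "For all efficacy analyses including time to all-cause mortality the treated set (on-treatment + 1 day) will be used".
- SAP 5.2.2 lists the endpoint as "Time to all-cause mortality occurring during the actual treatment period". SAP 6.1 defines that period as first intake to 1 day after last intake.
- SAP 6.8, item A, gives the censoring rule: "Patients with no event observed during the actual treatment period will be censored at date of last dose of randomized study drug administration", plus 1 day.

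Collection runs longer.

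- Protocol 5.1.2.3, for completed and discontinued patients alike: "vital status collection time of interest will be the planned 52-week + 21 days starting from visit 2". Protocol 7.1 says the same.
- SAP 6.1: "Patients that discontinue early will be monitored for exacerbations and vital status until they have reached the end of their planned study period". On its length: "The planned study period is defined as 360 days of treatment + 21 days of follow up".
- SAP 6.8 also defines a last known date alive: "The date of last known day alive is determined as the latest date among: the final vital status date", followed by a list of further dates. Item A does not use this date.

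Protocol 2.2 names survival as part of the secondary aim. Deaths are also reported outside the hazard ratio: SAP 7.8.1 tabulates by arm the fatal adverse events with onset up to last dose + 21 days, and SAP 7.8.2 lists every death with its investigator and adjudicated cause.

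**The concern.** A patient who takes the last dose and dies two or more days later is censored alive in the mortality hazard ratio, even though the trial has the date of death. Protocol 3.3.4.1 allows stopping for adverse events or other diseases, and its note on interruptions gives a hospital stay as an example. Drug stop can therefore be an early sign of death, whereas Cox and log-rank methods assume that censoring carries no such information.

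At stake is the only visible time-to-event comparison serving the survival aim. The by-arm fatal-event tables cover part of the gap, but they are counts rather than a time-to-event comparison, and they omit fatal events that start more than 21 days after the last dose.

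**Working it through.** **No stated mortality figure to reproduce.** The documents give no expected deaths, hazard ratio or power for mortality. The time-to-event sample size in Protocol 7.6 concerns first exacerbation and is not in dispute. It reproduces: the T+O event proportion is 1 − 0.35^0.88 = 0.603; Freedman's formula gives 3653 events; 3653/(0.65 + 0.603) gives 2916 per arm, against 2915 stated.

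**Step 1: days counted and not counted.** From SAP 6.1, planned treatment is 360 days and the planned study period is 360 + 21 = 381 days. A completer contributes 361 days. Assume that a share L of treatment days is lost and a share d of patients stops early. Average days per patient are then:

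- counted: 360(1 − L) + 1
- not counted, early stoppers: 360L + 20d
- not counted, completers: 20(1 − d)

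**Step 2: share of collected deaths left out.** Let the death hazard after an early stop be m times the on-drug hazard, with m = 1 for completers' follow-up days, and let the death risk be small. Then:

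share = [m(360L + 20d) + 20(1 − d)] / [360(1 − L) + 1 + m(360L + 20d) + 20(1 − d)]

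The part falling more than 21 days after last dose is m·360L over the same denominator. It is an upper limit for what the fatal-event tables miss, since a later death can stem from an event that began within the 21 days.

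L, d and m are all assumed. The 15% for L is borrowed from the patient-year information loss in Protocol 7.6, which is not defined there as off-drug time.

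| L, d | m | Share left out | More than 21 days after last dose |
|---|---|---|---|
| 5%, 10% | 1 | 38/381 = 10% | 18/381 = 5% |
| | 3 | 78/421 = 19% | 54/421 = 13% |
| | 5 | 118/461 = 26% | 90/461 = 20% |
| 15%, 30% | 1 | 74/381 = 19% | 54/381 = 14% |
| | 3 | 194/501 = 39% | 162/501 = 32% |
| | 5 | 314/621 = 51% | 270/621 = 43% |

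Using 364 treatment days instead of 360 changes each share by at most 0.001. With L = 15% and d = 20%, the shares left out are 19.4%, 38.2% and 49.9%.

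**Step 3: does leaving deaths out bias the comparison?** A simulation set the true ratio of death rates to 1.00, with average mortality of about 3% a year, 10% frail patients at 8 times the hazard of the rest, 12% stopping for other reasons over 360 days, and a given chance of stopping drug 2 to 60 days before death.

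| Chance of stopping before death, T+O / Tio | Ratio to last dose + 1 day | Ratio over 381 days |
|---|---|---|
| 40% / 40% | 1.00 | 1.00 |
| 30% / 40% | 1.16 | 1.00 |
| 40% / 50% | 1.19 | 1.00 |
| 30% / 50% | 1.38 | 1.00 |

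The on-treatment analysis counted 116 to 137 of about 235 deaths per 7800 patients. Bias appeared only when stopping before death differed between arms. Exchanging the arms would move the ratio the other way, for example 1/1.16 = 0.86.

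**Step 4: precision.** Take L = 15%, m = 1, 7800 patients and an assumed yearly mortality of 3%. Counted deaths rise from about 200 to 248, and the 99% confidence factor, exp(2 × 2.576/√deaths), falls from 1.44 to 1.39. At 2% it falls from 1.56 to 1.49, and at 4% from 1.37 to 1.33.

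**The case against.** The strongest reply is that the plan may already contain the analysis. Three visible signs point that way: SAP 6.8 shows an item A with no item B, the last-known-alive date serves no visible rule, and Table 6.1:2 has a planned-study-period column with no tick in any visible row. Parts of the public SAP are blacked out. This stands. A reader might infer that no mortality analysis over the full follow-up is planned; the documents do not support that.

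Second, the window is openly stated, identical in both documents and shared by all efficacy endpoints. It also has a rationale: Protocol 4.2.2.1 permits other LABA and LAMA products after treatment, which can blur the randomised contrast. This stands as a reason to keep the on-treatment analysis. There is no contradiction between protocol and SAP on the endpoint.

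Third, bias is not shown. The trial is double-blind with an active control, nothing in the documents suggests that stopping before death differs by arm, and an exacerbation alone is not a reason for withdrawal (Protocol 3.3.4.1). Some of the omitted time is also plain administrative follow-up: 18 of the 38 uncounted days in the 5%/10% case belong to completers. All of this stands and limits the point to a possibility of informative censoring. It does not explain why the visible survival comparison should set aside deaths that the trial takes trouble to collect and adjudicate.

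**Conclusion.** The point holds as a reporting gap in the visible definition. Deaths after last dose + 1 day are collected but do not enter the hazard ratio of the named endpoint, and the censoring may be informative. The shares of 10% to 51% rest on assumed discontinuation, lost time and off-drug hazard. They are not measures of bias.

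A reader might go further and conclude that the hazard ratio is biased, or that the declared endpoint must be replaced. The documents support neither: the size and direction of any bias cannot be derived, and the on-treatment question is legitimate. The hierarchy in Protocol 7.2 covers only the primary and key secondary tests, so no type I error claim changes. What remains is a low-cost improvement to the evidence behind the survival aim.

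**What to change.** In SAP 6.8 and 7.5.2, name a Cox/log-rank analysis of all deaths in treated patients over the planned study period.

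- Censor survivors at the last known date alive already defined in SAP 6.8, capped at one stated planned study end; deaths after the cap do not count.
- Reconcile the two end dates first: 360 + 21 = 381 days (SAP 6.1) and 52 weeks + 21 days = 364 + 21 = 385 days (Protocol 5.1.2.3).
- Report this analysis beside the last dose + 1 day analysis with equal prominence, and base any survival conclusion on both.
- If blacked-out text already contains this analysis, only give it that prominence.

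The cost is one extra analysis. The data are already collected, the period and the last-known-alive date are already defined, and the protocol's endpoint definition is left as it is. The downside is that off-drug time may include other LABA or LAMA treatment in either arm, which may dilute the contrast; that is why the on-treatment analysis stays.

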### 7.3.3 Safety analyses

All treated patients will be included in the safety analysis. In general, safety analyses will be descriptive in nature and will be based on BI standards. No hypothesis testing is planned prospectively.

Adverse events will be coded using the current version of the Medical Dictionary for Regulatory Activities (MedDRA) coding dictionary. Standard BI summary tables and listings will be produced to compare the incidence of adverse events across treatment groups. All adverse events with an onset after the first dose of trial medication and up to 21 days after the last dose of trial medication will be assigned to the on-treatment period. Other adverse events

Proprietary confidential information.

© 2015 Boehringer Ingelheim International GmbH or one or more of its affiliated companies. All rights reserved.

This document may not - in full or in part - be passed on, reproduced, published or otherwise used without prior written permission.

will be assigned either to the screening period, post-treatment period or the post-study period as appropriate.

Changes from baseline in vital signs and laboratory value will be summarised by treatment group and compared descriptively.

#### **7.3.4 Interim analyses**

No interim analysis is planned for this trial.

#### **7.3.6 Pharmacokinetic analyses**

No pharmacokinetic analyses are planned for this trial.

#### **7.3.7 Pharmacodynamic analyses**

No pharmacodynamic analyses are planned for this trial.

#### **7.3.8 Pharmacogenomic analyses**

No pharmacogenomic analyses are planned for this trial.

### **7.4 HANDLING OF MISSING DATA**

Since patients are followed up for exacerbations and vital status and the CAT questionnaire is an exploratory endpoint, missing data will not be imputed. Missing safety data will not be imputed with the exception of missing AE dates which will be imputed according to BI standards.

Randomly missing data (not due to worsening of disease or use of rescue medication) after inhalation for which there are data from that visit both before and after inhalations will be linearly interpolated. Randomly missing data with no subsequent non-missing values for that visit will be imputed using the last observation carried forward (LOCF) techniques prior to calculating AUC.

## 7.5 RANDOMISATION

Patients will be randomised in equal ratio to one of the two treatment groups in this trial and blocked randomisation will be used. Boehringer Ingelheim will generate the randomisation scheme and will prepare and code the medications to maintain the double-blind.

In order to maintain flexibility for drug supply, each individual medication kit will have a separate identification number. Assignment of medications at the clinic visits will be accomplished through the use of IRT. Each patient will be assigned a single randomisation number indicating the randomised treatment the patient will be on throughout the trial. BI will provide the randomisation and medication kit number lists to the IRT and the sites will access the IRT to obtain the randomisation number and medication kit numbers to be dispensed to the patient.

## 7.6 DETERMINATION OF SAMPLE SIZE

Based on a recent publication on the SPARK study (Wedzicha, et al, Lancet, 2013) and data from a previous BI study [REDACTED], the rate ratio and hazard ratio of moderate to severe COPD exacerbation between T+O FDCs and Tio 5 are assumed to be 0.88.

Assuming an annualised rate of moderate to severe COPD exacerbation for Tio 5 to be 0.85, a 12-month fixed study duration, two-sided type I error rate of 0.01 and 90% power, the sample size depends on the dispersion parameter for the negative binomial distribution. [Table 7.6: 1](#) gives the sample size estimations for a range of the dispersion parameters. In addition, assuming a 15% loss of information in patient-years, the estimated power corresponding to the sample size is also provided in the last column in Table 7.6: 1 below.

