### 7.3 PLANNED ANALYSES

#### 7.3.1 Primary analyses

The primary analysis includes all randomised patients who are documented to have received any dose of study medication, i.e., the primary analysis is performed using the treated set.

The primary endpoint, i.e., annualised rate of moderate to severe COPD exacerbation will be analysed using a negative binomial model including the fixed, categorical effect of treatment

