**Proprietary confidential information.**

© 2015 Boehringer Ingelheim International GmbH or one or more of its affiliated companies. All rights reserved.

This document may not - in full or in part - be passed on, reproduced, published or otherwise used without prior written permission.

Table 7.6: 1 Sample size estimations for annualised rate of moderate to severe COPD exacerbation under different dispersion parameters with 2-sided type I error rate of 0.01, 90% power, annual rate of 0.85 in Tio 5 and rate ratio = 0.88

Annual Rate in Tio 5 (r 1 )	Annual Rate in T+O FDC (r 2 )	r 2 /r 1	Dispersion Parameter	N per arm	Average exposure (months)	Total exposure adjusted for 15% loss of information (patient – years)	Power (after adjusting 15% loss of information in patient-years)
0.85	0.748	0.88	0.625 (SPARK)	3427	12	2913	85.8%
0.85	0.748	0.88	0.7	3563	12	3029	86.0%
0.85	0.748	0.88	0.8	3745	12	3184	86.2%
0.85	0.748	0.88	0.9	3927	12	3338	86.4%

The above calculation is based on the formulas in Zhu and Lakkis [P14-09564] and was calculated using the validated software package R. A sample size of 3900 patients per arm will give a power between 90% to 94% under different dispersion parameters to detect a rate ratio of 0.88 between T+O FDC and Tio 5 in the annualised rate of moderate to severe COPD exacerbation assuming the annual rate in Tio 5 is 0.85 and two-sided type I error rate of 0.01. After adjusting for a 15% loss of information in patient-years and the same assumptions as above, a sample size of 3900 patients per arm will give a power between 86.1% to 90.6%

Assuming the proportion of patients who had at least one moderate to severe COPD exacerbation within 1 year in the Tio 5 arm is 0.65, a hazard ratio between T+O FDC and Tio 5 of 0.88, a two-sided type I error rate of 0.01 and power of 90%, the estimated sample size for time to the first moderate/severe COPD exacerbation is 2915 patients per arm (using nQuery Advisor 7.0). A sample size of 3900 patients per arm will give a power of 97% using the same assumptions.

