A sample size of 3900 patients per arm or 7800 patients in total is selected for this trial because it provides acceptable power to detect a 12% reduction in annualised rate of moderate to severe COPD exacerbation of T+O FDC as compared with Tio 5 using a two-sided type I error rate of 0.01, under a reasonable range of dispersion parameters of the negative binomial distribution and assuming the annual rate in Tio 5 is 0.85. This sample size also gives sufficient power to detect a 12% reduction in the hazard rate of moderate to severe COPD exacerbation of T+O FDC as compared to Tio 5 at a two-sided type I error rate of 0.01 and assuming the proportion of patients who had at least one moderate/severe COPD exacerbation after 1 year in the Tio 5 arm is 0.65.

Proprietary confidential information.

© 2015 Boehringer Ingelheim International GmbH or one or more of its affiliated companies. All rights reserved.

This document may not - in full or in part - be passed on, reproduced, published or otherwise used without prior written permission.

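### The 97% power for the key secondary rests on a hazard ratio of 0.88 that does not follow from section 7.6's own negative binomial model, under which a rate ratio of 0.88 implies a first-event hazard ratio of about 0.90

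*Protocol*

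**What the plan says.** All of the following is in protocol section 7.6 unless noted.

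- One value serves both effect measures: "the rate ratio and hazard ratio of moderate to severe COPD exacerbation between T+O FDCs and Tio 5 are assumed to be 0.88". It is attributed to a published trial and an earlier sponsor study.
- The primary calculation opens with "Assuming an annualised rate of moderate to severe COPD exacerbation for Tio 5 to be 0.85, a 12-month fixed study duration", and uses a "two-sided type I error rate of 0.01 and 90% power". Table 7.6:1 gives one dispersion value per row (0.625, 0.7, 0.8, 0.9) and the corresponding N per arm (3427, 3563, 3745, 3927).
- The key secondary calculation assumes that 65% of Tio 5 patients have at least one event within a year, with a hazard ratio of 0.88. It needs 2915 per arm for 90% power, and then: "A sample size of 3900 patients per arm will give a power of 97% using the same assumptions".
- The closing justification of 3900 per arm refers to adequate primary power "under a reasonable range of dispersion parameters of the negative binomial distribution" and adds: "This sample size also gives sufficient power to detect a 12% reduction in the hazard rate of moderate to severe COPD exacerbation", again with 65% in the control arm.

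The analyses match this split. Under protocol section 7.3.1 the "annualised rate of moderate to severe COPD exacerbation will be analysed using a negative binomial model including the fixed, categorical effect of treatment". Under section 7.3.2 a "Cox's proportional hazard model will be used to estimate the hazard ratio and the corresponding 99% confidence intervals", with the p-value from the log-rank test. The GENMOD code in SAP section 7.4 fits a single dispersion parameter across arms.

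**The concern.** A patient free of a first exacerbation is a patient with a count of zero. The count model used for the primary endpoint therefore also fixes the 12-month event-free proportion in each arm, and hence the ratio of cumulative first-event hazards. When patients differ in their underlying rates, high-rate patients have their first event early. Those still at risk become more alike across arms, and the first-event hazard ratio moves towards 1. A rate ratio and a first-event hazard ratio of the same size is what a Poisson model gives, not a negative binomial model with dispersion 0.625 to 0.9.

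The key secondary is the second and last test in the confirmatory hierarchy (protocol section 7.2, SAP section 7.5.1), and its power is cited in support of the sample size. The risk of missing a real effect is stated as 3%. If the primary model is right it is considerably larger, and a reader interpreting a non-significant key secondary would be working from the wrong figure.

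**Working it through.** **Inputs (protocol section 7.6).** Rates r1 = 0.85 and r2 = 0.88 × 0.85 = 0.748; 12 months; k = 0.625, 0.7, 0.8, 0.9; two-sided alpha 0.01 (z = 2.576); 90% power (z = 1.282); 3900 per arm; key secondary hazard ratio 0.88 and control event proportion 0.65. ln(0.88) = −0.1278.

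**1. Reproduce the primary table.** N per arm = (2.576 + 1.282)² × (1/r1 + 1/r2 + 2k) / ln(0.88)². This gives 3427, 3563, 3745 and 3927, matching Table 7.6:1. The term 2k is one dispersion shared by both arms.

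**2. Reproduce the key secondary figures.** The T+O event proportion is 1 − 0.35^0.88 = 0.603. Freedman's formula gives (2.576 + 1.282)² × (1.88/0.12)² ≈ 3652 events. Dividing by 0.65 + 0.603 gives 2915 per arm, as stated. At 3900 per arm there are 3900 × 1.253 = 4887 events. Power is Φ(√4887 × 0.12/1.88 − 2.576) = Φ(1.886) = 97.0% (97.1% with Schoenfeld's formula). The arithmetic is right for these inputs.

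**3. First-event hazard ratio implied by the primary model.** The zero-count probability is S(r) = (1 + k·r)^(−1/k). The 12-month cumulative hazard ratio is ln(1 + 0.748k) / ln(1 + 0.85k). For k = 0.625 this is ln(1.4675)/ln(1.53125) = 0.3836/0.4261 = 0.900. This step uses only the zero-count probability and a common k.

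A Cox model estimates an average over follow-up. Reading the negative binomial as a gamma-mixed Poisson process, each arm's first-event hazard at time t is r/(1 + k·r·t). The ratio starts at 0.88 and rises to 0.918-0.928 at one year. Solving the expected Cox score equation gives the averages in the table.

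**4. Power at 3900 per arm.** Power = Φ(√D/2 × |ln HR| − 2.576), with HR the Cox average and D the expected events.

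- *Hazard ratio changed, 65% kept:* for k = 0.625, D = 3900 × (0.65 + 1 − 0.35^0.898) = 4916, and Φ(70.11/2 × 0.1074 − 2.576) = Φ(1.190) = 88.3%.
- *Event proportions also from the model:* for k = 0.625, D = 3900 × (0.494 + 0.459) ≈ 3716, and Φ(60.96/2 × 0.1074 − 2.576) = Φ(0.698) = 75.8%.

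| k | Cumulative HR | Cox average HR | Event proportion, Tio 5 / T+O | Power, HR only changed | Power, HR and event proportions from model |
|---|---|---|---|---|---|
| 0.625 | 0.900 | 0.898 | 49.4% / 45.9% | 88.3% | 75.8% |
| 0.7 | 0.902 | 0.900 | 48.7% / 45.2% | 87.1% | 73.3% |
| 0.8 | 0.904 | 0.902 | 47.7% / 44.4% | 85.4% | 70.0% |
| 0.9 | 0.906 | 0.904 | 46.8% / 43.6% | 83.7% | 66.8% |

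Simulated log-rank tests from the same model (4000 trials, 3900 per arm, full 12 months) gave 75.5% at k = 0.625 and 67.4% at k = 0.9, agreeing with the last column. N per arm for 90% power would be about 4090 to 4590 with 65% kept, or about 5410 to 6410 fully model-based.

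**5. The 65% is a second mismatch.** At a mean of 0.85, even a Poisson model gives only 1 − exp(−0.85) = 57.3% with an event, and the negative binomial gives 46.8-49.4%. At k = 0.625, the hazard ratio alone takes power from 97% to 88%, the event proportion alone takes it to 91%, and both together take it to 76%.

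**The case against.** Three arguments on the other side have weight.

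*The calculation is correct as stated.* A reader might infer that the 97% is an arithmetical error. It is not: step 2 reproduces it, and the closing sentence of section 7.6 is true on its own terms, because it is conditional on a 12% hazard reduction and a 65% event proportion. This stands. The point concerns consistency between inputs.

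*The two 0.88s are not strictly incompatible.* A reader might infer that both cannot hold. That needs a common dispersion. Negative binomial counts also arise when each event raises the risk of the next, a mechanism that protocol section 3.3 itself describes. If event risk is a + b × (previous events), with b equal in both arms, the rate ratio equals the first-event hazard ratio and the dispersions differ by 1/0.88. For example, take k = 0.625 for Tio 5 and 0.710 for T+O. The cumulative hazards are ln(1.53125)/0.625 = 0.682 and ln(1 + 0.710 × 0.748)/0.710 = 0.600, a ratio of 0.88. Both dispersions lie inside the tabulated range. This stands as a possibility, but it is not the model the plan uses: Table 7.6:1 and the SAP code each have one dispersion for both arms. Nor does it restore the 97%. The event proportions would be 1 − exp(−0.682) = 49.4% and 1 − exp(−0.600) = 45.1%, giving 3900 × 0.945 ≈ 3687 events and power Φ(60.7/2 × 0.1278 − 2.576) ≈ 90%.

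*The hazard ratio is attributed to outside data.* Protocol section 1.1 says earlier effects varied between time to first exacerbation and annual rate. The documents therefore do not show that 0.88 is a poor estimate of the hazard ratio. They show only that it does not follow from the rate ratio under the sizing model.

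**Conclusion.** The concern holds as an internal inconsistency of moderate importance. Under the model that section 7.6 uses for the primary endpoint, with a dispersion common to both arms, a rate ratio of 0.88 corresponds to a first-event hazard ratio of about 0.90. Key secondary power at 3900 per arm is then about 67-76% on fully consistent inputs. The hazard ratio by itself accounts for a fall from 97% to 84-88%, but those figures retain a 65% event proportion that the same model does not produce, so they isolate one effect and should not be offered as the corrected power.

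The results assume full 12-month follow-up and, for the Cox average, the gamma-mixed Poisson reading of event timing. The 15% information loss that section 7.6 applies to the primary is not applied to the 97% and is not in these figures either.

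A reader might go further and infer that the trial is undersized or its error control compromised. The documents do not support that: N is driven by the primary endpoint, whose table reproduces, and the key secondary is tested only after the primary at the same alpha.

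**What to change.** In protocol section 7.6, restate key secondary power with the hazard ratio and event proportions derived from the rates and dispersions in Table 7.6:1: about 67-76% across the tabulated dispersions. Show 84-88% beside it as the effect of the hazard ratio alone.

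If a hazard ratio of 0.88 and a 65% event proportion are to be kept, say that they are separate assumptions that do not follow from the primary model with a common dispersion, give their basis, and label the 97% as conditional on them. Qualify the closing sentence on sufficient power in the same way.

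The change is one paragraph. Sample size, alpha and testing order stay as they are; the cost is a less favourable stated power for the key secondary.
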